12.2 Health Economics Analysis

For this secondary health economic endpoint, health care utilization (number and length of hospitalizations and unscheduled cardiovascular-related visits), the total number and length of hospitalizations will be summarized by treatment groups in the ITT population.

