**Schedule of Examinations**

**Table 1. Summary of Subject Assessments:**

Assessments	BL D0 	M3 D76- 104	M6 D166- 210	M9 D240 -300	Y1 D330 -420	M18 D480 -600	Y2 D630 -809	M30 D810- 989	Y3 D990- 1170	UNS
Clinic visit	X	X	X		X		X		X	X
Phone follow-up 				X		X		X		
Patient Information and Consent	X									
Medical history	X									
HATCH score	X	X	X		X		X		X	X
ECG 	X	X	X		X		X		X	X
TTM 		X	X	X	X	X	X	X	X	X
TEE 	X									
TTE 	X				X		X		X	
QoL (EQ-5D, AFEQT) 	X	X	X		X		X		X	
Health status 	X	X	X		X		X		X	X
Cardiac medication	X	X	X	X	X	X	X	X	X	X
Adverse events		X	X	X	X	X	X	X	X	X
Cardioversion / re-ablation documented		X	X	X	X	X	X	X	X	X

1. Phone follow-up calls include check for AEs, changes in cardiac medication and TTM.
2. To be collected if completed as standard of care.
3. Dispensation of TTM device at Month 3. Additional details/instructions regarding TTM monitoring are provided below.
4. Only for patients randomized to PVI, within 48 hours pre-procedure.
5. TTE to be performed within 30 days pre-treatment. For the Test Group, TTE must be repeated prior to discharge
6. AFEQT questionnaire is only to be completed by a subpopulation due to limited validated translations
7. LA Size, blood pressure, NYHA Functional Classification of heart disease, Diabetes, lipid profile, renal function and dementia.
8. Day 0 Test Group (PVI)= Index ablation procedure and Day 0 Control Group (AAD) = Randomization

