#### Health Economics (HE) Outcomes:

- Health care utilization (number and length of hospitalizations and unscheduled cardiovascular-related visits).
- Quality of Life (QoL) at 3 months, 6 months, 1 year, 2 years and 3 years by EQ-5D and AFEQT Questionnaire and change from baseline.

Note: AFEQT Questionnaire will only be used in validated languages and therefore, only distributed to a subgroup of the study population. The AFEQT questionnaire is validated in following languages:

French, German, Italian, Spanish (Spain), Spanish (US), Polish, Czech, Simplified Chinese (China), Traditional Chinese (Taiwan), Dutch, Korean, Norwegian, Swedish.

---

d Baseline presence of dementia would preclude subject enrolment in this study; however, new onset dementia could occur during the course of the study. If the dementia became sufficiently serious to preclude continued adherence to protocol requirements (Section 9.6), an Investigator may decide to terminate this subject from the study.

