### **11.2.2 Unscheduled Visits**

If a subject returns for a cardiovascular related visit outside of the protocol-defined visit schedule provided in Table 1, the visit will be considered "unscheduled" (UNS). If the

unscheduled visit is for a repeat ablation procedure, the protocol follow-up schedule will be based on the index procedure. For all cardiovascular related unscheduled visits, an unscheduled visit eCRF must be completed and the subject must also return for his/her next scheduled study visit.

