### 13.4 Sample Size and Power Calculation

A total sample size of 322 (161:161) subjects will be required to ensure 85% power to detect the effect size measured by negative log of the hazard ratio equal to 1.154f (treatment group over control group). This calculation assumes a 50% cross-over rate from the AAD group to the ablation group, a 10% drop-out rate in each group over the 3 year follow-up period, and 1.5 years accrual time. This calculation is based upon one-sided superiority testing with alpha equal to 0.025. Using meta-analysis, the rates of disease progression at the end of follow-up are estimated to be 25% and 5% in the AAD and ablation group, respectively (see the point estimate justification document for details, Appendix C). The sample size calculation is based upon the method developed by Rubinstein, Gail and Santner (RGS,1981) and also incorporates group sequential design with multiple interim looks.

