14.2.8	ITT, PP	New AAD Drugs – ATC classes	16.2.22	
14.2.9	ITT, PP	Heart Rhythm	16.2.17.3	
14.2.10.1	ITT, PP	Factors Associated With Time to Persistent AF/AT Results of Cox models with single baseline covariates	16.2.17.1	
14.2.10.2	ITT, PP	Factors Associated With Time to Persistent AF/AT Results of Cox model with multivariate baseline covariates	16.2.17.1	
14.2.10.3	PP	Factors Associated With Time to Persistent AF/AT Results of Cox models with single baseline covariates and treatment as time-dependent covariate	16.2.17.1	
14.2.10.4	PP	Factors Associated With Time to Persistent AF/AT Results of Cox model with multivariate baseline covariates and treatment as time-dependent covariate	16.2.17.1	
14.2.11.1	PP	Quality of Life – EQ5D Descriptive summary of VAS	16.2.14	
14.2.11.2	PP	Quality of Life – EQ5D	16.2.14	

Table Number	Population	Table Title / Summary	Supporting Listing	Interim Analysis Number
		Descriptive summary of changes from baseline in VAS		
14.2.11.3	PP	Quality of Life – EQ5D Results of repeated measurement model for changes from baseline in VAS	16.2.14	
14.2.11.4	PP	Quality of Life – EQ5D Frequency table for EQ-5D single items	16.2.14	
14.2.11.5	PP	Quality of Life – EQ5D Frequency table for changes from baseline in EQ-5D single items and results of Wilcoxon-Mann-Whitney test	16.2.14	
14.2.12.1	PP	Quality of Life – AFEQT Descriptive summary of derived scores	16.2.13	
14.2.12.2	PP	Quality of Life – AFEQT Descriptive summary of changes from baseline	16.2.13	
14.2.12.3	PP	Quality of Life – AFEQT Results of repeated measurement model	16.2.13	
14.2.13.1	ITT	Health Economic Analysis Number of hospitalizations	16.2.25	
14.2.13.2	ITT	Health Economic Analysis Length of hospitalizations	16.2.25	
14.2.13.3	ITT	Health Economic Analysis	16.2.25	

Table Number	Population	Table Title / Summary	Supporting Listing	Interim Analysis Number
		Number of unscheduled cardiovascular-related visits		

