15.2 Planned Listing Descriptions

The following are planned data and subject listings for protocol 144 (09-Apr-2013). Listings will number according to the nomenclature used to support the clinical study report. Listings will be ordered by treatment group and subject and timepoint. In addition to the unique subject identification, the treatment group will be displayed on all listings.

It is indicated in the last column which listings will also be produced for interim analysis.

Listing Number	Population	Listing Title / Summary	Interim Analysis
16.2.1	All Subjects	Study Population Status for Each Subject	
16.2.2	ITT	Inclusion/Exclusion Criteria for Each Subject	
16.2.3	ITT	Study Completion Status and Discontinued Subjects	
16.2.4.1	Screening Failures	Reason for Screening Failures	
16.2.4.2	ITT	Protocol Deviations Reported in CRF	
16.2.4.3	ITT	Major Protocol Deviations and Exclusions from Analysis Populations	
16.2.5	ITT	Visit Dates Including Days since Randomization	
16.2.6	ITT	Subject Demographics	
16.2.7	ITT	Cardiovascular Medical History	
16.2.8	ITT	Other Relevant Medical History	
16.2.9	ITT	Prior Procedure History	
16.2.10	ITT	AF History	
16.2.11	ITT	Cardiovascular Medication History	
16.2.12	ITT	Screening Examination Done (Yes/No)	

Listing Number	Population	Listing Title / Summary	Interim Analysis
16.2.13	ITT	AFEQT Questionnaire	
16.2.14	ITT	EQ-5D Questionnaire	
16.2.15	ITT	Ablation Procedures	
16.2.16	ITT	Baseline Medication Optimization	
16.2.17.1	ITT	Primary Endpoint: Time to Persistent AF/AT	3.1
16.2.17.2	ITT	CEC Adjudication Form	
16.2.17.3	ITT	Secondary Endpoints - Number of repeat ablations and new anti-arrhythmic drugs and heart rhythm	
16.2.18	ITT	Follow-Up Visits – Assessments Performed	
16.2.19	ITT	Blood Pressure	
16.2.20	ITT	NYHA Classification and Additional Diagnoses	
16.2.21	ITT	HATCH Score	
16.2.22	ITT	Cardiovascular Medication	
16.2.23	ITT	Adverse Events	3.2
16.2.24	ITT	Serious Adverse Events Form	
16.2.25	ITT	Unscheduled Cardiovascular Visit/Hospitalization	
16.2.26	ITT	12-Lead ECG	
16.2.27	ITT	Holter Monitoring	
16.2.28	ITT	Event Recorder	
16.2.29	ITT	Transesophageal Echocardiogram	
16.2.30	ITT	Transthoracic Echocardiogram	
16.2.31	ITT	Cardioversion	

Listing Number	Population	Listing Title / Summary	Interim Analysis
16.2.32	ITT	Medication Management	

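### Health-care utilization is sourced only from the unscheduled-visit/hospitalization listing, so first ablations count differently by arm for visits and, as the source suggests but no rule states, for admissions

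*SAP*

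**What the plan says.** The protocol's health-economic endpoint (section 10.2) covers the number and length of hospital stays and cardiovascular visits outside the schedule. It does not say whether stays for ablation count. SAP 12.2 adds no rule: "the total number and length of hospitalizations will be summarized by treatment groups in the ITT population".

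SAP 15.1 plans three tables: 14.2.13.1 ("Health Economic Analysis Number of hospitalizations"), 14.2.13.2 (length of stay) and 14.2.13.3 (unscheduled cardiovascular visits). Each names listing 16.2.25, "Unscheduled Cardiovascular Visit/Hospitalization", as its only support. Ablation procedures have a separate listing, 16.2.15, which no utilization table cites.

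Protocol 11.2.2 decides what is unscheduled: "If a subject returns for a cardiovascular related visit outside of the protocol-defined visit schedule provided in Table 1", the visit is classed as unscheduled. It adds that "For all cardiovascular related unscheduled visits, an unscheduled visit eCRF must be completed" and treats a repeat ablation as one such visit. Note 8 to Table 1 fixes the start of each arm's schedule: "Day 0 Test Group (PVI)= Index ablation procedure and Day 0 Control Group (AAD) = Randomization". Protocol 11.2.1 keeps Control subjects who cross over on their existing schedule.

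SAP section 7 keeps cross-over subjects in Control for ITT. The protocol (13.14.1) had planned utilization in the per-protocol population, where cross-overs count in Test; SAP 8.1 changed this to ITT.

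**The concern.** An ITT utilization table should describe what each strategy consumes. The Test strategy begins with an ablation. If that procedure is left out for Test because it was scheduled, while the same procedure in a Control cross-over is counted because it was not, the total describes neither strategy. Equal follow-up time would not remove the difference.

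The imbalance runs in the direction of an expected benefit: Appendix A of the protocol anticipates fewer hospital stays after ablation. The move from per-protocol to ITT matters here because it places cross-over admissions in Control without adding a rule for the index stay. At stake is the reading of a listed secondary endpoint.

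**Working it through.** The plan gives no utilization figure, so there is nothing to reproduce. The check has two parts.

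**Which ablations reach listing 16.2.25**

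| Procedure | Status under the protocol | In unscheduled visits (14.2.13.3)? | In hospitalizations (14.2.13.1 and .2)? |
|---|---|---|---|
| Test index ablation | Day 0 of the schedule (Table 1, note 8) | No | Not stated; the listing title suggests not |
| Test repeat ablation | Unscheduled (11.2.2) | Yes | Not stated; the listing title suggests yes |
| Control cross-over ablation | Outside the unchanged Control schedule (11.2.1, 11.2.2) | Yes | Not stated; the listing title suggests yes |

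For visits, the asymmetry follows from the protocol's definitions. For hospitalizations, it is inferred from the title of the only cited source. The index procedure does seem to involve a stay, since Table 1 (note 5) requires a repeat echocardiogram in Test subjects before discharge.

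**Size of the effect on admissions per subject**

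Inputs from the documents:
- Cross-over rate *c* = 0.50. Protocol 13.4: "This calculation assumes a 50% cross-over rate from the AAD group to the ablation group".
- 161 subjects per arm (protocol 13.4).

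Assumptions, because the documents give no figures:
- One admission per ablation, and every Test subject ablated.
- *r* repeat ablations per Test subject, from 0 to 0.3.
- *hT* and *hC* are other admissions per subject, with *hT* - *hC* between 0 and -0.5.
- *c* is also varied down to 0.10.

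Test minus Control:
- As sourced: (*hT* + *r*) - (*hC* + *c*)
- Every ablation counted: (1 + *hT* + *r*) - (*hC* + *c*)
- Every ablation excluded: *hT* - *hC*

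At *c* = 0.50, 0.50 × 161 = 80.5, so about 80 Control cross-over ablations would be counted and up to 161 Test index ablations would not.

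| *c* | *r* | *hT* - *hC* | As sourced | All counted | All excluded | Sign reverses? |
|---|---|---|---|---|---|---|
| 0.10 | 0 | 0 | -0.10 | +0.90 | 0 | Yes |
| 0.25 | 0 | 0 | -0.25 | +0.75 | 0 | Yes |
| 0.50 | 0 | 0 | -0.50 | +0.50 | 0 | Yes |
| 0.50 | 0.3 | 0 | -0.20 | +0.80 | 0 | Yes |
| 0.25 | 0.3 | 0 | +0.05 | +1.05 | 0 | No |
| 0.50 | 0 | -0.5 | -1.00 | 0.00 | -0.5 | No (tie when all counted) |

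Subtracting the first formula from the second leaves 1 in every row. The size of the shift therefore does not depend on *c*, *r* or other use. The sign reverses only when Test's as-sourced advantage lies between 0 and 1 admission per subject.

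**The case against.** A reader might infer that the plan excludes the index stay from hospitalizations by rule. The documents do not support that. The slash in the title of listing 16.2.25 could mean unscheduled visits or any hospitalization, SAP 12.2 refers to the total without exclusions, and the eCRF is not among the documents. This objection stands for tables 14.2.13.1 and 14.2.13.2. It does not reach 14.2.13.3, where the protocol's definitions decide.

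The separate ablation listing proves nothing by itself. Listing 16.2.15 covers the ITT population and is not limited to Test, so having its own listing would take a cross-over ablation out of 16.2.25 as readily as an index ablation. The argument has to rest on scheduling. Protocol 11.2.2 names repeat ablations and not cross-overs, but a cross-over ablation still meets its general definition.

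A reader might also infer that the comparison must reverse. It need not: Test repeat ablations go on the same form, and the table above contains cases without reversal. Nor is the 50% a forecast. It is a sample-size assumption, and Appendix B aims for cross-over well below published rates. Protocol 9.5 also allows for Test subjects who never have a catheter inserted, so the shift is at most 1.0 per randomized Test subject under the one-admission assumption.

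Finally, use after the assigned first treatment is a legitimate question, with a cross-over ablation seen as a consequence of starting on drugs. That is fair, but the SAP does not say it is asking that question. The planned counts of cross-overs (table 14.1.7.1) and repeat ablations (table 14.2.5) help a reader but do not supply the missing index stays.

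**Conclusion.** The point holds in this form. SAP 12.2 does not say how index, repeat and cross-over ablations enter utilization, and its single source treats first ablations differently by arm. For unscheduled visits this follows from the protocol. For hospitalizations it is the natural reading of the cited listing, but it is not documented.

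With one admission per ablation, every Test subject ablated, equal other use and no repeats, the planned 50% cross-over gives -0.5 as sourced and +0.5 with all ablations counted. The firmer result is the gap of about 1 admission per ablated Test subject between the two rules; the reversal is conditional. This should be corrected before the utilization tables are read as a comparison of strategies. The endpoint is descriptive, and the primary test and its alpha do not depend on it.

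**What to change.** In SAP 12.2, state one rule for ablation stays and visits, applied to both arms from randomization. Link listing 16.2.15 to 16.2.25 by subject and date, so that cross-over and repeat ablations already in 16.2.25 are not counted twice. Show each of tables 14.2.13.1 to 14.2.13.3 in two ways:

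- (a) with every index, repeat and cross-over ablation included;
- (b) with every one excluded.

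Version (a) of table 14.2.13.3 needs a label saying that it includes the scheduled index procedure. If the index length of stay was not recorded, give (a) for counts only and use (b) for length of stay. The features of the first ablation listed in SAP 9.4 include no admission or discharge dates, so their availability must be checked first.

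The change resolves the matter under either reading of the listing title. It costs some SAP wording, a linkage of two planned listings and one extra presentation per table. The result may be less favourable to ablation.

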### 3.0 Protocol Summary

Title:	Atrial Fibrillation Progression Trial (ATTEST)
Design:	This is a prospective, multi-center, randomized (1:1), controlled, two-arm, open-label, clinical study.
Objective:	The objective of this study is to determine whether in subjects with Paroxysmal AF (PAF), early RF ablation treatment using the THERMOCOOL ® Catheter Family in conjunction with the CARTO ® 3, CARTO ® XP or CARTO ® RMT System, delays progression of AF compared with drug therapy (either rate or rhythm control) using current AF management guidelines. 
Enrollment:	Up to 330 subjects will be enrolled in this study.
Clinical Sites:	Up to 50 sites primarily in Europe, and/or Asia and/or North America.
Subject Population:	PAF patients with recurrent AF for at least 2 years who have failed at least 1 but no more than 2 prescribed drugs (either anti-arrhythmic or rate control drug)  Eligible subjects who sign the study informed consent form will be randomized into one of two study arms:
PVI (Test) Group:	RF ablation to achieve pulmonary vein isolation (PVI) using the THERMOCOOL ® Catheter Family in conjunction with the CARTO ® 3, CARTO ® XP or CARTO ® RMT System
Drug Therapy (Control) Group:	AAD therapy (either rate or rhythm control) using current AF management guidelines 
Primary Endpoint:	Time to persistent AF/AT (excluding isthmus-dependent atrial flutter) at 3 years. Persistent AF/AT is defined as AF/AT lasting longer than 7 consecutive days or requiring termination by cardioversion after 48 hours. a
Secondary Endpoints:	Rate to persistent AF/AT; Number of repeat ablations and new AAD drugs; Rhythm (% subjects in SR, % subjects with recurrent AF); Pre-existing or new onset/worsening condition(s) that may be associated with AF progression; Catheter-related complications (ablation), adverse drug reactions (AAD); Health care utilization and Quality of Life.
Study Duration:	4.5 years (18 months enrollment period and 3 years follow-up per subject)

---

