2.2.3 Health Economic and Quality of Life Endpoints

The health economic endpoints are:

- Health care utilization (number and length of hospitalizations and unscheduled cardiovascular-related visits)
- Quality of Life (QoL) at 3 months, 6 months, 1 year, 2 years, and 3 years by change from baseline in
 - EQ-5D Score
 - AFEQT Score (collected in a subset of countries)

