5. CHANGES TO PLANNED ANALYSIS

5.1 Changes for the final analysis

As the study was terminated early, without having met primary effectiveness or futility criteria at the most recent interim analysis, it is not fully obvious which alpha level to use for the primary efficacy analysis. However as the number and time points of the interim analyses had not been fixed in advance, it was decided to spend all alpha remaining for the final analysis, in other words to spend what is left from the total alpha. Moreover, after further discussion, it has been decided to update the calculation of the primary endpoint to use procedure date as start date for time to event calculation rather than randomization date (see section 8.3).

It also was decided to delete some of the analyses originally planned in the protocol:

- For secondary endpoint “factors associated with AF disease progression”, only the main analyses will be performed, and some of the supporting models were deleted
- Analysis of site heterogeneity will not be performed

Moreover, a sensitivity analysis for the primary endpoint and first secondary endpoint was added, using an alternative definition for the primary endpoint based on the consensus statement of the HRS (Heart Rhythm Society, 2017).

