8.3 Derived Variables

Duration of AF [months]

Time between the recorded date of first AF and the date of randomization.

Time to persistent AF/AT

According to protocol, persistent AF/AT is defined as AF/AT lasting longer than 7 consecutive days or requiring termination by cardioversion after 48 hours. The primary endpoint is reached at the date of the first cardioversion after randomization (except cardioversion solely as part of a (re-)ablation procedure) or detection of persistent AF/AT by transtelephonic monitoring (TTM, performed between month 3 and month 36). The sponsor will review and adjudicate all events (progressions to persistent AF/AT), which were reported by the Investigator. Adjudication will already be performed for the interim analyses. All events where the sponsor confirmed in their final assessment that the primary endpoint was reached will be taken into account for analysis. The date at which the primary endpoint was reached will be taken as adjudicated by the sponsor or as reported by the Investigator (if no sponsor adjudicated date is available).

The protocol is not specific about the start date for time to event calculation. Originally according to SAP version 1.0 (which was applied for the interim analyses) time to event had been defined as the difference between randomization date and the date at which the endpoint was reached. However, after further discussion, it was decided to update the start date for time to event calculation for final analysis and to use date of procedure as start date for the test group, and date of randomization as start date for the control group.

This approach seems to be more appropriate and more conservative, as visit windows are calculated from date of procedure for test group. Otherwise, if time to event was calculated from date of randomization, test group would have longer follow-up period and longer time to each follow-up visit as control group.

If the primary endpoint is not observed during follow-up time, subjects will be regarded as censored at the completion visit/ last visit or at the last time TTM was recorded, whichever is later.

Time to persistent AF (HRS 2017)

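### Health-care utilization is summarised by arm without adjustment for follow-up time and without a stated counting window

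*SAP*

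**What the plan says.** SAP 12.2 (Health Economics Analysis) is the whole analysis text for this endpoint. It states that "the total number and length of hospitalizations will be summarized by treatment groups in the ITT population". The table list in SAP 15.1 gives three ITT tables, 14.2.13.1 to 14.2.13.3: hospitalizations, their length, and unscheduled cardiovascular visits. None is titled as a rate. Protocol 13.16 specifies descriptive statistics for the endpoint.

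Three other places bear on follow-up time:

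- **Day 0.** Footnote 8 of Protocol Table 1 sets it differently by arm. For Test it is the ablation, and for Control it is randomization: "Index ablation procedure and Day 0 Control Group (AAD) = Randomization".
- **Start date.** SAP 8.3 (Derived Variables) changes the time-to-event start date for the final analysis, "to use date of procedure as start date for the test group, and date of randomization as start date for the control group". Its reason is that, with randomization as the start, "test group would have longer follow-up period and longer time to each follow-up visit as control group".
- **Early end.** SAP 5.1 opens: "As the study was terminated early, without having met primary effectiveness or futility criteria at the most recent interim analysis".

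SAP 8.3 applies its correction to time to persistent AF/AT. No section extends it, or any other exposure adjustment, to utilization.

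**The concern.** Admissions, hospital days and unscheduled visits accumulate with time under observation. If one arm is observed longer, it collects more of them at the same underlying rate. If subjects are observed for unequal times, a total per subject no longer describes a 3-year burden.

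The log-rank test takes account of censoring for the primary endpoint. Nothing comparable is planned here. The SAP's own reasoning on start dates shows that the visit schedule can make observation time differ by arm, and that schedule governs all data collection.

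The index-ablation stay adds a second ambiguity. Each treated Test subject has a procedure, and the protocol requires a repeat TTE before discharge. If that stay counts, it could add up to one hospitalization per treated Test subject that says nothing about later morbidity. The SAP does not say whether it counts.

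At stake is how readers interpret a descriptive secondary comparison. The primary result is not affected.

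**Working it through.** The documents state no utilization figure, so there is nothing of the plan's own to reproduce. The check asks how far unadjusted totals per subject would differ between arms if the true event rates were equal and constant. Under that condition, the Test/Control ratio of expected totals equals the ratio of mean observation times.

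**Inputs from the documents**
- Planned follow-up: 36 months from Day 0 (Protocol 3.0 and Table 1).
- Planned accrual: 18 months (Protocol 3.0), so the planned end is month 18 + 36 = 54 after study start.
- Day 0: procedure for Test, randomization for Control.

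**Assumptions, because the documents give no figure**
- Wait d from randomization to procedure: 0.5, 1, 2 or 3 months.
- Common calendar stop C: month 48, 42 or 36, compared with full follow-up.
- Uniform accrual, with no drop-out modelled.

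**Formulas.** For a subject randomized at month e, observed months are:
- Control: min(36, C − e)
- Test counted from randomization: min(36 + d, C − e)
- Test counted from the procedure: min(36, C − e − d)

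Each is averaged over e from 0 to 18. With full follow-up the ratio is (36 + d)/36 when both arms are counted from randomization, and 36/36 when each is counted from its own Day 0.

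Worked example for C = 48, d = 3:
- Control subjects randomized after month 12 are cut short, so the Control mean is 36 − 6²/(2 × 18) = 35.
- Test subjects randomized after month 9 are cut short, so the mean loss is 9²/(2 × 18) = 2.25 months.
- Test from randomization: 39 − 2.25 = 36.75, and 36.75/35 = 1.050.
- Test from the procedure: 36 − 2.25 = 33.75, and 33.75/35 = 0.964.

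**Results: Test/Control ratio for d = 0.5 / 1 / 2 / 3 months**

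| Stop | Mean Control months | Both arms from randomization | Each arm from its Day 0 |
|---|---|---|---|
| Full follow-up | 36 | 1.014 / 1.028 / 1.056 / 1.083 | 1.000 throughout |
| Month 48 | 35 | 1.009 / 1.018 / 1.035 / 1.050 | 0.995 / 0.990 / 0.978 / 0.964 |
| Month 42 | 32 | 1.005 / 1.010 / 1.017 / 1.023 | 0.989 / 0.978 / 0.955 / 0.930 |
| Month 36 | 27 | 1.000 throughout | 0.981 / 0.963 / 0.926 / 0.889 |

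The share of Control subjects with less than 36 months is 33%, 67% and 100% for stops at months 48, 42 and 36.

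The table shows three things:
- An earlier common stop shrinks the imbalance counted from randomization, and removes it when every subject is truncated.
- The same stop creates the opposite imbalance if each arm is counted from its own Day 0.
- Dividing by observed patient-time gives a ratio of 1.00 in every cell under these assumptions.

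**The case against.** A reader might infer that the SAP declares Test follow-up to be longer, that totals therefore penalise Test, and that the arms cannot be compared. The documents do not support this stronger reading, for these reasons:

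- The sentence in SAP 8.3 is conditional. It describes what would follow if time ran from randomization, and it concerns the time-to-event endpoint. Counted from Day 0, planned follow-up is 3 years in both arms.
- Early termination does not by itself favour an arm. A common stop date truncates both, and it reduces the imbalance counted from randomization.
- SAP 8.1 makes N, mean, SD, median, range and quartiles the default for quantitative variables. The tables may therefore show distributions per subject and need not be bare group sums.
- The sample-size sections assume 10% drop-out in each group. Nothing supports a differential rate.
- The endpoint is descriptive, so a formal rate model goes beyond what the protocol requires.

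All of this stands, and it limits the size and direction of the point. The core remains: a mean per subject is still unadjusted for exposure. Neither the start nor the end of counting is stated, and the equal 3-year window is no longer assured once a trial stops early.

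**Conclusion.** The point holds as a low-cost improvement. Utilization is to be compared by randomized arm with no allowance for follow-up time and no defined window, although the SAP recognised the Day 0 difference and dealt with it for the time-to-event endpoint.

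The likely distortion is modest and of uncertain sign. Unadjusted Test totals per subject would be 0 to 8% too high if counted from randomization. Counted from each arm's Day 0 with a common stop at months 36 to 48, they would be about 0.5 to 11% too low. These ranges rest on assumed waits and stop dates, uniform accrual, and equal constant event rates. The SAP gives no termination date and no number of subjects with shortened follow-up, so the actual figure cannot be derived from the documents. The ranges do not include any effect of counting the index-ablation stay.

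**What to change.** In SAP 12.2:

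1. Count from randomization to last contact in both arms. This keeps events during the wait for ablation, and it gives a start date to Test subjects who are in the ITT population but never have the procedure.
2. Report hospitalizations, hospital days and unscheduled cardiovascular visits per patient-year, with total follow-up time by arm.
3. Show the hospitalization results with and without the index-ablation stay.
4. Keep the planned totals alongside, since a single rate per patient-year hides any change in event rate over time.

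A rate-ratio model, such as a negative binomial with log follow-up as offset, is optional because the protocol asks only for descriptive statistics. The change needs a few lines of code on data that the trial already holds. The downside is one more table.
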